6.12. Subgroup Analyses

Subgroup analyses of PFS and OS will be performed for each of following potential prognostic subgroup variables:

- All baseline stratification factors
- nonsteroidal aromatase inhibitor received at cycle 1 (letrozole versus anastrozole)
- Disease setting (de novo metastatic versus recurrent metastatic versus locoregionally recurrent)
- Measurable disease at baseline (yes versus no)
- Number of organs involved (1 versus 2 versus 3+)
- Age (<65 years versus ≥65 years)
- Region (North America, Europe, Asia, and Other)
- Race (Caucasian, Asian, and Other)
- PgR status (positive versus negative)
- Baseline ECOG PS (0 versus 1).

If a level of a factor consists of fewer than 10% of randomized patients, analysis within that level will be omitted.

Analyses will be done within subgroup and, separately, across subgroups with a test of interactions of subgroups with treatment performed. Estimated HRs and CIs for the within subgroup analyses will be presented as a forest plot along with p-values for tests of interactions between subgroup variables and treatment.

Other subgroup analyses may be performed as deemed appropriate. If any safety analyses identify important imbalances between arms, subgroup analyses of these endpoints may be performed.

6.13. Protocol Violations

Significant protocol violations that potentially compromise the data integrity and patients' safety will be summarized by treatment group for all randomized patients. These violations will include deviations which can be identified programmatically and those which can only be identified by the clinical research associate (CRA) during monitoring. Significant protocol deviations are described in another document within the study Trial Master File.

6.14. Interim Analyses and Data Monitoring

6.14.1. Safety Interim Analyses

The Data Monitoring Committee (DMC) is responsible for providing external oversight of patient safety in Study JPBM independently of the Lilly study team and Lilly Global Product Safety (GPS).

During the study, safety interim analyses will be performed every 3 months. The first safety interim analysis will be triggered by the 90th patient enrolling, with the data cutoff for this analysis occurring 1 month after the trigger. The safety interim analyses will be conducted to evaluate the overall safety profile of abemaciclib when given in combination with NSAIs.

Each safety evaluation will be based, at least, on the following data reports:

- summary of treatment discontinuations and reasons for discontinuation
- summary of SAEs
- summary of TEAEs
- summary of CTCAE graded central laboratory results
- Lilly Safety System reports for all patients with SAEs
- summary of drug exposure and dose adjustments (including delays and reductions) and reasons for adjustment
- listing of treatment discontinuations due to adverse event or death.

Details pertaining to the conduct of these analyses are provided in the JPBM DMC Charter.

6.14.2. Efficacy Interim Analyses

One efficacy interim analysis of PFS and 3 interim analyses of OS are planned, as described in Sections 6.7.2.2 and 6.7.3.3. The interim PFS analysis (and corresponding OS analysis) will be conducted by the DMC. All other efficacy analyses will be conducted by the sponsor.

Rules for unblinding the sponsor at an interim analysis can be found in the protocol.

At the time of the interim PFS analysis, analyses of PFS and OS provided to the DMC will include:

- the boundary values for significance,
- the p-value for a stratified log rank test comparing the two treatment arms, stratified by the randomization factors,
- an estimate of the HR between the two arms based on a Cox proportional hazards model, stratified by the randomization factors, and
- a KM analysis by treatment arm.

Details pertaining to the conduct of these analyses are provided in the JPBM DMC Charter.

6.14.3. Pharmacokinetic/Pharmacodynamic Interim Analyses

A limited number of preidentified individuals independent of the study team may receive access to unblinded data, as specified in the unblinding plan, prior to the interim or final database lock, in order to initiate the final population PK model development processes for interim or final PK and PD analyses. Information that may unblind the study during the analyses will not be reported to study sites or blinded study team until the study has been unblinded. These analyses will be described in a separate document.

6.15. Analyses for the Japanese Regulatory Authority

Analyses conducted specifically for the Pharmaceuticals and Medical Devices Agency (PMDA) will be described in a separate SAP.

6.16. Annual Report Analyses

Annual report analyses, including Developmental Safety Update Report (DSUR) and Investigational Brochure (IB) analyses, are described in the LY2835219 Program Safety Analysis Plan.

6.17. Clinical Trial Registry Analyses

Additional analyses will be performed for the purpose of fulfilling the Clinical Trial Registry (CTR) requirements.

Analyses provided for the CTR requirements include the following:

- Summary of AEs, provided as a dataset which will be converted to an XML file. Both SAEs and ‘Other’ AEs will be summarized by: treatment group, MedDRA PT.
- An AE is considered ‘Serious’ whether or not it is a treatment emergent adverse event (TEAE).
- An AE is considered in the ‘Other’ category if it is both a TEAE and is not serious. For each SAE and ‘Other’ AE, for each term and treatment group, the following are provided:
 - the number of participants at risk of an event
 - the number of participants who experienced each event term
 - the number of events experienced.
- Consistent with www.ClinicalTrials.gov requirements, ‘Other’ AEs that occur in fewer than 5% of patients/subjects in every treatment group may not be included if a 5% threshold is chosen (5% is the minimum threshold).
- Adverse event reporting is consistent with other document disclosures for example, the clinical study report (CSR), manuscripts, and so forth.

In addition, a participant flow will be created that will describe how many enrolled patients completed the study, and for those who did not, the frequency of each reason for not completing.

This analysis will be based on study discontinuation, not treatment discontinuation. A patient will be identified as having completed the study if the patient dies while on the study or the patient had discontinued study treatment and is in follow up at the time of the final OS analysis. Patients who withdraw consent before the final OS analysis or who are still on treatment at the time of the final OS analysis will be identified as not completing the study.

Redacted Version

7. Unblinding Plan

Randomization will occur using an IWRS system. Assignment to treatment groups will be determined by a computer-generated random sequence. Security measures will be taken so that treatment group code that can link patients to study arm will be blinded in the database.

In order to maintain the scientific integrity of this double-blind trial, access to study data will be strictly controlled prior to the interim and final analyses of OS. Dummy treatment assignment will be used in the reporting database until the database lock for the final analysis of overall survival. During this time, analyses using unblinded treatment codes will be performed only at the interim analysis points specified in the protocol/SAP. For those safety and efficacy analyses assigned to the DMC, only the designed Statistical Analysis Center (SAC), who is independent of the sponsor, will perform analyses on unblinded data. For the interim PK analysis to occur prior to the interim/primary PFS analyses, the list of individuals that will have access to unblinded data will be provided with the PK/pharmacodynamic analysis plan, and documentation concerning their access to the data will be retained.

Data sets will be created for the purpose of aggregate data review by the sponsor in which treatment assignment is scrambled so that personnel involved in the day-to-day conduct of the trial and development and validation of analysis programs will be blinded to patient treatment assignment.

While every effort will be made to blind both the patient and the investigator to the identity of the treatment, the inadvertent unblinding of a patient may occur. This unblinding will not be sufficient cause (in and of itself) for that patient to be excluded from any safety or efficacy analyses.

8. Changes to Planned Analyses in Protocol

Version 1 of the SAP does not contain any significant changes in planned analyses compared to the original protocol.

Version 2 of the SAP does not contain any significant changes in planned analyses compared to Protocol Amendment (a).

Version 3 of the SAP does not contain any significant changes in planned analyses compared to Protocol Amendment (b).

Redacted Version

9. References

- Agresti A. Categorical Data Analysis. 2nd ed. New York: Wiley, 2002.

Appendix 1. Abemaciclib Consolidated AE Terms

Redacted Version

Consolidated Term / Consolidated Body System	CTCAE Preferred Terms
Abdominal pain / Gastrointestinal disorders	Abdominal discomfort, Abdominal pain, Abdominal pain lower, Abdominal pain upper, Gastrointestinal pain
Anaemia / Blood and lymphatic system disorders	Anaemia, Haematocrit decreased, Haemoglobin decreased, Red blood cell count decreased
Breast pain / Reproductive system and breast disorders	Breast discomfort, Breast pain
Cardiac failure / Cardiac disorders	Cardiac failure, Cardiac failure congestive
Conjunctival haemorrhage / Eye disorders	Conjunctival haemorrhage, Eye haemorrhage
Conjunctivitis / Infections and infestations	Conjunctivitis, Eye infection
Depression / Psychiatric disorders	Depressed mood, Depression
Ear infection / Infections and infestations	Ear infection, Otitis media
Ear pain / Ear and labyrinth disorders	Ear discomfort, Ear pain
Eye pain / Eye disorders	Eye pain, Ocular discomfort
Fatigue / General disorders and administration site conditions	Asthenia, Fatigue
Folate deficiency / Metabolism and nutrition disorders	Anaemia folate deficiency, Folate deficiency
Gastroenteritis / Infections and infestations	Gastric infection, Gastroenteritis, Gastroenteritis viral, Gastrointestinal infection
Haematuria / Renal and urinary disorders	Blood urine present, Haematuria
Hot flush / Vascular disorders	Flushing, Hot flush
Hypercalcaemia / Metabolism and nutrition disorders	Blood calcium increased, Hypercalcaemia
Hypercholesterolaemia / Metabolism and nutrition disorders	Blood cholesterol increased, Hypercholesterolaemia
Hyperglycaemia / Metabolism and nutrition disorders	Blood glucose increased, Hyperglycaemia
Hyperkalaemia / Metabolism and nutrition disorders	Blood potassium increased, Hyperkalaemia
Hypermagnesaemia / Metabolism and nutrition disorders	Blood magnesium increased, Hypermagnesaemia
Hypernatraemia / Metabolism and nutrition disorders	Blood sodium increased, Hypernatraemia
Hyperphosphataemia / Metabolism and nutrition disorders	Blood phosphorus increased, Hyperphosphataemia
Hypertension / Vascular disorders	Blood pressure diastolic increased, Blood pressure increased, Blood pressure systolic increased, Hypertension
Hypertriglyceridaemia / Metabolism and nutrition disorders	Blood triglycerides increased, Hypertriglyceridaemia
Hypoalbuminaemia / Metabolism and nutrition disorders	Blood albumin decreased, Hypoalbuminaemia
Hypocalcaemia / Metabolism and nutrition disorders	Blood calcium decreased, Hypocalcaemia, Calcium deficiency
Hypoglycaemia / Metabolism and nutrition disorders	Blood glucose decreased, Hypoglycaemia
Hypokalaemia / Metabolism and nutrition disorders	Blood potassium decreased, Hypokalaemia
Hypomagnesaemia / Metabolism and nutrition disorders	Blood magnesium decreased, Hypomagnesaemia
Hyponatraemia / Metabolism and nutrition disorders	Blood sodium decreased, Hyponatraemia
Hypophosphataemia / Metabolism and nutrition disorders	Blood phosphorus decreased, Hypophosphataemia

Consolidated Term / Consolidated Body System	CTCAE Preferred Terms
Hypotension / Vascular disorders	Blood pressure diastolic decreased, Blood pressure decreased, Blood pressure systolic decreased, Hypotension
Intestinal obstruction / Gastrointestinal disorders	Gastrointestinal obstruction, Intestinal obstruction, Large intestinal obstruction, Small intestinal obstruction
Iron deficiency / Metabolism and nutrition disorders	Blood iron decreased, Iron deficiency
Leukocytosis / Blood and lymphatic system disorders	Leukocytosis, White blood cell count increased
Leukopenia / Blood and lymphatic system disorders	Leukopenia, White blood cell count decreased
Lung infection / Infections and infestations	Lung infection, Pneumonia
Lymphocytosis / Blood and lymphatic system disorders	Lymphocytosis, Lymphocyte count decreased
Lymphopenia / Blood and lymphatic system disorders	Lymphopenia, Lymphocyte count decreased
Myocardial infarction / Cardiac disorders	Acute myocardial infarction, Myocardial infarction
Nephrolithiasis / Renal and urinary disorders	Nephrolithiasis, Ureterolithiasis
Neuropathy / Nervous system disorders	Acute polyneuropathy, Anaesthesia, Axonal neuropathy, Burning sensation, Dysaesthesia, Hypoaesthesia, Neuralgia, Neuritis, Neuropathy peripheral, Paraesthesia, Peripheral sensory neuropathy, Polyneuropathy, Sensory disturbance, Sensory loss, Skin burning sensation, Toxic neuropathy
Neutropenia / Blood and lymphatic system disorders	Neutropenia, Neutrophil count decreased
Oropharyngeal pain / Respiratory, thoracic and mediastinal disorders	Oropharyngeal discomfort, Oropharyngeal pain
Rash / Skin and subcutaneous tissue disorders	Exfoliative rash, Mucocutaneous rash, Rash, Rash erythematous, Rash follicular, Rash generalized, Rash macular, Rash maculo-papular, Rash maculovesicular, Rash morbilliform, Rash papular, Rash papulosquamous, Rash pruritic, Rash vesicular, Vulvovaginal rash
Thrombocytopenia / Blood and lymphatic system disorders	Platelet count decreased, Thrombocytopenia
Tracheitis / Infections and infestations	Tracheitis, Viral tracheitis
Urinary tract infection / Infections and infestations	Cystitis, Urinary tract infection
Urticaria / Skin and subcutaneous tissue disorders	Urticaria, Urticaria papular

Leo Document ID = 5420af9c-d790-4c2e-9dee-53f280cdb1c0

Approver: [REDACTED]
Approval Date & Time: 14-Apr-2017 16:09:31 GMT
Signature meaning: Approved

Redacted Version

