6.11.2. Adverse Events

Adverse event (AE) terms and severity grades will be assigned by the investigator using Common Terminology Criteria for Adverse Events (CTCAE) Version 4. In addition, AE verbatim text will also be mapped by the sponsor or designee to corresponding terminology within MedDRA. Adverse events will be reported using the following reporting process:

- The CTCAE Version 4 term reported by the investigator will be mapped to the MedDRA PT and system organ class (SOC) of the corresponding MedDRA lower level term (LLT), unless the reported CTCAE term is ‘Other – specify’.
- If the reported CTCAE term is ‘Other – specify’ the MedDRA LLT, PT and SOC mapped from the verbatim AE term will be used.
- Preferred terms identified by Medical as clinically identical or synonymous will be grouped together under a single consolidated PT. For example, ‘Asthenia’ and ‘Fatigue’ will be reported as ‘Fatigue.’ See [Appendix 1](#) for a complete listing. This listing may be updated prior to database lock as new synonymous terms are observed.
- All listings and summaries will use the PT resulting from this process.

Pre-existing conditions are defined as AEs that begin prior to the first dose of study drug.

A treatment emergent adverse event (TEAE) is defined as any AE that begins between the day of first dose and 30 days after treatment discontinuation (or up to any time if serious and related to study treatment), or any pre-existing condition that increases in CTCAE grade between the day of first dose and 30 days after treatment discontinuation (or up to any time if serious and related to study treatment). Comparisons of pre-existing conditions to on-treatment events at the LLT level will be used in the treatment-emergent computation.

A serious adverse event (SAE) is any AE during this study that results in one of the following outcomes:

- death
- initial or prolonged inpatient hospitalization
- a life-threatening experience (that is, immediate risk of dying)
- persistent or significant disability/incapacity
- congenital anomaly/birth defect
- considered significant by the investigator for any other reason.

Important medical events that may not result in death, be life-threatening, or require hospitalization may be considered SAEs when, based on appropriate medical judgment, they may jeopardize the patient and may require medical or surgical intervention to prevent one of the outcomes listed in this definition.

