To assess the relationship of the AE to the study treatment, the following terminologies are defined (in Protocol Section 8.1.2):

- **Related:** a direct cause and effect relationship between the study treatment and the AE is likely.
- **Possibly related:** a cause and effect relationship between the study treatment and the AE has not been demonstrated at this time and is not probable, but is also not impossible.
- **Unrelated:** without question, the AE is definitely not associated with the study treatment.

As per Lilly's standard operating procedures (SOPs), all "related" and "possibly related" AEs and SAEs will be defined as related to study treatment.

The following TEAE/SAE listings and summaries will be produced:

- Overview of TEAEs
- Summary of TEAEs by PT (all grade and grade ≥ 3)
- Summary of TEAEs by SOC and PT (all grade and grade ≥ 3)
- Summary of TEAEs by PT and maximum grade (1-5)
- List of SAEs
- Summary of SAEs by SOC and PT (all grade and grade ≥ 3).

The four summaries will be produced for all TEAEs/SAEs and repeated for TEAEs/SAEs related to study treatment.

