6.11.4. Clinical Laboratory Evaluation

All relevant hematology and chemistry laboratory values will be graded according to CTCAE Version 4. These calculated grades will be summarized by cycle and maximum post-baseline grade over the entire study.

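### SAP Appendix 1 puts *Lymphocyte count decreased* under two opposite consolidated terms, Lymphocytosis and Lymphopenia

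*SAP*

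**What the plan says.** SAP Section 6.11.2 sets out how adverse event terms are derived for reporting. Its consolidation step reads: "Preferred terms identified by Medical as clinically identical or synonymous will be grouped together under a single consolidated PT". It refers to Appendix 1 for the full list and adds: "This listing may be updated prior to database lock as new synonymous terms are observed". It then makes the result binding: "All listings and summaries will use the PT resulting from this process".

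Three rows of Appendix 1 matter here, all under Blood and lymphatic system disorders:

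- Lymphocytosis: "Lymphocytosis, Lymphocyte count decreased"
- Lymphopenia: "Lymphopenia, Lymphocyte count decreased"
- Leukocytosis, for comparison: "Leukocytosis, White blood cell count increased"

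The Revision History (SAP Section 3) records that the list came in with Version 3 and was updated in Version 4 after medical review of observed events.

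**The concern.** A falling lymphocyte count is the opposite of lymphocytosis, so the Lymphocytosis row cannot satisfy the SAP's own test of clinical identity or synonymy. Listing the same preferred term in the next row also breaks the requirement for a single consolidated term.

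This is more than a cosmetic matter because Appendix 1 is an operative specification. It feeds the listings and summaries of treatment-emergent and serious adverse events by preferred term, including those by maximum grade. A literal implementation could show low-lymphocyte events, with their grades, as Lymphocytosis and could understate Lymphopenia.

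**Working it through.** No power, alpha or sample-size figure is involved. The check is a full read of the Appendix 1 table and then a trace of where the mapping is used.

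**Step 1: is any preferred term mapped more than once?** All rows were transcribed and counted.

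| Item | Count |
|---|---|
| Consolidated terms (rows) | 49 |
| Preferred-term entries | 139 |
| Distinct preferred terms | 138 |
| Terms listed under more than one consolidated term | 139 − 138 = 1 |

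The one repeated term is *Lymphocyte count decreased*, under Lymphocytosis and Lymphopenia. *Lymphocyte count increased* appears nowhere in the table.

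**Step 2: does the direction agree with the name?** Of the 49 rows, 25 contain a term ending in *increased* or *decreased*. In 24 of them the direction fits the consolidated name, for example *increased* under Hyperkalaemia and *decreased* under Hypokalaemia. The exception is Lymphocytosis: 25 − 24 = 1.

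**Step 3: compare the neighbouring white-cell pair.**

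| Consolidated term | Count term listed | Direction fits? |
|---|---|---|
| Leukocytosis | White blood cell count increased | Yes |
| Leukopenia | White blood cell count decreased | Yes |
| Lymphocytosis | Lymphocyte count decreased | No |
| Lymphopenia | Lymphocyte count decreased | Yes |

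Both lymphocyte rows are complete, with term, body system and preferred terms intact. This does not look like a broken table or a redaction.

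**Step 4: what would a literal program do?** Let C, L and D be the sets of patients with events coded as Lymphocytosis, Lymphopenia and Lymphocyte count decreased.

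| Handling of the duplicate | Lymphocytosis row | Lymphopenia row |
|---|---|---|
| Intended | C | L ∪ D |
| Event copied to both rows | C ∪ D | L ∪ D |
| First match only | C ∪ D | L |
| Last match only | C | L ∪ D |

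Two of the three literal readings put D under Lymphocytosis, and one of those also removes it from Lymphopenia.

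**Step 5: how far does it reach?**

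- *Affected if programmed literally:* the preferred-term listings and summaries in Section 6.11.2. The same would hold for the treatment-emergent and serious event summaries sent to the data monitoring committee (Section 6.14.1) and the registry tables by preferred term (Section 6.17), so far as they use the consolidated terms. The registry tables count events as well as patients, so copying an event to both rows could inflate the event counts there.
- *Not affected:* patient counts by system organ class and in the overview, because both rows share one body system. Treatment emergence is decided at the lower-level-term stage (Section 6.11.2), so the set of qualifying events does not change.
- *Not affected:* the laboratory summaries in Section 6.11.4, which grade the measured values directly: "These calculated grades will be summarized by cycle and maximum post-baseline grade over the entire study". The committee also receives a graded central laboratory summary. Neither depends on Appendix 1.
- *Not affected:* all efficacy analyses.

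**The case against.** The strongest reply is that this is a copying slip that the SAP's own rule already overrides. A programmer who applies the synonymy requirement would not send a decrease to Lymphocytosis, and a one-to-one lookup would expose the duplicate. The lookup itself is not in the documents, so no actual misreporting is shown. Low lymphocytes would still be visible in the graded laboratory results, and the list may be updated before database lock.

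Most of this stands as a limit on the harm. None of it makes the row right. The contradiction is in the approved text even though the list had already been through a medical review. The update provision is tied to newly observed synonymous terms, so it offers a route to a correction but does not supply one. The laboratory summaries are separate outputs and do not correct an adverse event table. It is also fair to say that *increased* is an inference from the Leukocytosis row, although a strong one. That *decreased* does not belong under Lymphocytosis needs no inference.

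**Conclusion.** The concern holds, as a minor point. One of 138 distinct preferred terms is mapped twice, and one of 25 directional rows is reversed. Two preferred-term lines, Lymphocytosis and Lymphopenia, could be misreported. These counts show that the slip is isolated; they do not measure its effect on the results. The documents give no rate for these events, so the number misplaced cannot be stated. Any effect depends on the appendix having been programmed as written, which the documents do not show either way.

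**What to change.** In the Lymphocytosis row, replace *decreased* with *increased*, in line with the Leukocytosis row, after the medical team has confirmed that this was the intended term. Add a check that each preferred term maps to exactly one consolidated term. Confirm whether the programmed lookup carries the error, and rerun earlier safety tables only if they used the faulty mapping.

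The cost is a one-word correction and a short check of the lookup table. If the database has not been locked, the change can go in with a list update, recorded as a correction because it is not a newly observed synonym. If it has been locked, the correction and any rerun tables should be documented in the clinical study report.
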